Description of Interventions:	
a) The Na-APR-1 (M74) candidate vaccine contains recombinant Na-APR-1 (M74) adsorbed onto aluminum hydroxide gel (Alhydrogel®) and suspended in a solution containing 10mM imidazole, 150mM sodium chloride and 0.3% Empigen BB, with pH 7.4 ± 0.1. The final concentrations of Na-APR-1 (M74) and Alhydrogel® in the drug product are 0.1mg/ml and 0.8mg/ml, respectively. Doses of 10, 30 and 100 µg Na-APR-1 (M74) will be delivered IM to the deltoid by injecting different volumes of the 0.1mg/ml preparation.b) The Na-GST-1 candidate vaccine contains the recombinant Na-GST-1 adsorbed onto Alhydrogel® and suspended in a solution containing 10mM imidazole and 10% glucose. The final concentrations of Na-GST-1 and Alhydrogel® in the drug product are 0.1mg/ml and 0.8mg/ml, respectively. Only one dose of Na-GST-1 will be tested (100µg), at a volume of 1.0ml delivered IM to the deltoid.c) Gluco-Pyranosylphospho-Lipid A Aqueous Formulation (GLA-AF) is a Toll-like Receptor-4 agonist. Point-of-injection formulations with this immunostimulant will be prepared immediately prior to vaccination by adding an appropriate volume of GLA-AF to Na-APR-1 (M74) and withdrawing an appropriate volume to administer the desired amount of Na-APR-1 (M74) plus 5µg GLA-AF IM to the deltoid.d) The ENGERIX-B hepatitis B vaccine will serve as the comparator vaccine. Each 0.5 ml dose contains 20 µg recombinant hepatitis B surface protein expressed by

Saccharomyces cerevisiae and adsorbed to aluminum hydroxide will be injected IM to the deltoid.

- e) To maintain the study blind by ensuring that all subjects receive two injections at each vaccination point, sterile normal saline (0.9%) for injection will be co-administered to those subjects randomized to receive Hepatitis B vaccine.

Objectives:

Primary:

Safety

1. To evaluate the safety and reactogenicity of three different dose concentrations of *Na-APR-1* (M74)/Alhydrogel® co-administered with *Na-GST-1*/Alhydrogel® in healthy Gabonese children.

Secondary:

Immunogenicity

1. To determine the doses of co-administered *Na-APR-1* (M74) and *Na-GST-1* that result in the highest levels of IgG antibody approximately 14 days after the third vaccination.

Tertiary:

Immunogenicity

1. To assess and compare the duration of the antibody responses of *Na-GST-1* and *Na-APR-1* (M74).

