1.2.2 Rationale for Doses and Dose Schedule to be Studied

Na-APR-1 (M74)/Alhydrogel® and *Na-GST-1*/Alhydrogel® (with or without GLA-AF) have been tested at the same field site as that proposed in the study described in this protocol, in healthy hookworm-exposed adults without any observed safety concerns. Therefore, in the study described in this protocol, these two vaccine products will be administered in escalating doses, to school-age children who live in an area where hookworm is endemic. Doses of 10, 30 and 100 µg of *Na-APR-1* (M74) and *Na-GST-1*/Alhydrogel® were selected for evaluation based on preclinical studies and to maintain an equal fold-increase in the amount of antigen. The 10 µg dose was also selected as the lowest dose for clinical trials due to the difficulty in precisely dispensing lower volumes (both vaccine antigens have been formulated at a protein concentration of 100µg/ml). Selection of the maximum 100 µg doses of *Na-GST-1* and *Na-APR-1* (M74) is based on the safety and immunogenicity data from the Phase 1 studies of these antigens that have been conducted in adults, in which this was the maximum dose tested.

To date, up to 100 µg *Na-APR-1* (M74)/Alhydrogel® administered with 5 µg GLA-AF has been very well tolerated in healthy adults, with no observed vaccine-related Serious Adverse Events and only mild to moderate local injection site pain and tenderness being the most commonly reported adverse events. However, the addition of GLA-AF to *Na-GST-1*/Alhydrogel did not significantly increase IgG levels to the *Na-GST-1* antigen. Therefore, GLA-AF will not be tested further in combination with *Na-GST-1*/Alhydrogel.

For the study proposed in this clinical protocol, each child will be vaccinated three times, on Days 0, 56, and 112 or 180. On each vaccination day each child will receive two injections, one injection per arm. This vaccination schedule was selected to coordinate with the Expanded Program on Immunization as the human hookworm vaccine is intended to target children, including eventually infants. Two different vaccination schedules are being tested (i.e., 0, 2, 4 months vs. 0, 2, 6 months) to determine the optimal immunogenicity.

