3 STUDY DESIGN

The study will be conducted as a randomized, placebo-controlled, double-blind Phase 1 dose-escalating clinical trial in healthy children between the ages of 6 and 10 years, inclusive, living in the hookworm-endemic area of Lambaréné, Gabon. The study is designed to evaluate the safety, reactogenicity, and immunogenicity of Na-GST-1/Alhydrogel® co-administered with Na-APR-1 (M74)/Alhydrogel®, as compared to the hepatitis B vaccine, in this age group.

Prior to beginning study-related activities, the consent and cooperation of representative community members will be sought, after which parents of potential pediatric participants will be invited to learn about the study and consent to the participation of their child. After a parent or legal representative provides written informed consent for the child's participation and passes the informed consent comprehension questionnaire, the child will undergo eligibility screening, including a complete medical history, physical examination, hematology testing, liver and renal function testing, HIV antibody testing, Hepatitis B and C serology, and urinalysis. In addition, a fecal examination will be performed for ova and parasites, and urine will be examined for *S. haematobium* ova. All clinically significant abnormalities will be reviewed with parents/legal guardians and referral of the child for follow-up care will be provided. After screening, those children determined to be eligible, based on the inclusion and exclusion criteria, will be invited to participate in the study.

Sixty children will be progressively enrolled into 1 of 3 Groups over a projected 3-month enrollment period, with each child followed for 9 months after the final injection (i.e., until Study Day 380 for those receiving vaccinations according to a 0,2,4-month schedule and until Study Day 448 for those receiving vaccinations according to a 0,2,6-month schedule). Group enrollment will be done in an open sequential fashion, whereas within each Group, investigational product (IP) assignment and vaccination will be done in a randomized double-blind fashion.

60 subjects will be enrolled into 3 groups of 20:

The first 20 subjects will be recruited and enrolled into Group 1:

- Group 1 double-blind IP allocation (n=20):
 - 16 subjects will receive 10µg Na-APR-1 (M74) plus 5µg GLA-AF delivered by IM injection in the deltoid muscle, with 10µg Na-GST-1 administered IM in the alternate arm.

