4.3.2 Allocation of vaccination schedule and vaccine randomization

Within each cohort the first 10 participants will receive the 0,2,4-month vaccination schedule and the last 10 will receive the 0,2,6-month schedule. The participants will be randomized to either the experimental group, receiving *Na-APR-1*(M74) plus 5 µg GLA-AF co-administered with *Na-GST-1*, or randomized to the control group who will receive HBV co-administered with sterile saline. In addition, there will be a randomization to assign left/right arm vaccination for the first injection, the arms will be alternated for the second and third sets of vaccinations. The Randomization list will thus only be used on Day 0 for a particular participant.

The vaccination manager assigns the Study ID when the vaccines are being prepared for that particular participant. The Study ID is written onto the syringes and then the vaccinator writes the Study ID onto the CRF.

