4.3.3 Masking Procedures

Due to the staggered, dose-escalation design of the trial, it will not be possible to blind to *Na-APR-1* (M74)/Alhydrogel® or *Na-GST-1*/Alhydrogel® dose assignment. That is, those subjects enrolled into Groups 1 and 2 will receive either 10µg *Na-APR-1* (M74)/Alhydrogel® administered to one arm and 10µg *Na-GST-1*/Alhydrogel® administered to the alternate arm, or the hepatitis B vaccine in one arm and sterile saline administered to the alternate arm. Subjects enrolled into Groups 3 and 4 will receive either 30µg *Na-APR-1* (M74)/Alhydrogel® administered to one arm and 30µg *Na-GST-1*/Alhydrogel® administered to the alternate arm, or the hepatitis B vaccine in one arm and sterile saline administered to the alternate arm, and so on.

Investigators and subjects will be blinded to the within-Group random allocation to receive co-administered *Na-APR-1* (M74)/Alhydrogel® and *Na-GST-1*/Alhydrogel® or co-administered hepatitis B vaccine and sterile saline until all subjects have completed their Day 208 visit, the safety and secondary immunogenicity outcomes (i.e., anti-*Na-GST-1* and anti-*Na-APR-1* [M74] IgG antibody results by ELISA) have been monitored and entered into the database, and the database has been “soft-locked” for interim analysis. Procedures to maintain blinding include administering two injections to all subjects at each vaccination point. For this, sterile saline will be co-administered to those subjects randomized to receive the hepatitis B vaccine.

The study vaccine manager and his assistant will prepare all investigational product doses (vaccine or sterile saline placebo) in a separate room, and will hand filled syringes to the vaccinator(s). Since the 10 and 30µg doses of the *Na-APR-1* (M74) and *Na-GST-1* formulations are of different volumes than that of hepatitis B vaccine, the contents of all syringes will be disguised using opaque tape. As a further precaution, the vaccinator(s) will not be involved in assessments of reactogenicity or adverse events.

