2. Frequency of study vaccine-related serious adverse events from the time of the first study vaccination through approximately 9 months after the last study vaccination.
3. Frequency of clinical safety laboratory adverse events.
4. Frequency of unsolicited adverse events, graded by severity, from the time of each study vaccination through approximately 1 month after each study vaccination.
5. Frequency of new-onset chronic medical conditions through approximately 9 months after the third study vaccination.
6. Frequency of Adverse Events of Special Interest through approximately 9 months after the third study vaccination.

Analysis Plan:

- a. The proportion of participants with at least one injection site AE will be compared by vaccine and dose cohort. We will test the null hypotheses that the type and number of adverse events is the same across all groups by Fisher's exact test.
- b. Laboratory results (hematological and clinical chemistry) will be examined for trends over time and any clinically significant values for individuals will be reported.

Secondary Objective: To determine the doses of co-administered Na-APR-1 (M74) and Na-GST-1 that result in the highest levels of IgG antibody approximately 14 days after the third vaccination.

Secondary Outcome Measure:

The following parameters will be evaluated for each dose of Na-APR-1 (M74) co-administered with Na-GST-1:

1. The IgG level by a qualified indirect ELISA approximately 14 days after the third vaccination.

Analysis Plan:

- a. The proportion of participants with detectable anti-Na-GST-1 and anti-Na-APR-1 (M74) responses will be summarized as a descriptive measure.
- b. IgG levels will be displayed graphically by study group using notched box plots.
- c. Geometric mean antibody responses will be compared between vaccine formulation and dose groups. Comparisons between groups will be made by a one-way analysis of variance (ANOVA) with pair-wise comparisons between groups made by contrasts.
- d. Geometric mean antibody responses for each antigen will be compared using a regression model with main effects for the doses of Na-APR-1 (10, 30 or 100 μ g), and Na-GST-1 (10, 30 or 100 μ g).

Tertiary Objective 1: To assess and compare the duration of antibody responses to Na-GST-1 and Na-APR-1 (M74).

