Tertiary Outcome Measure 1: The IgG antibody response, by indirect enzyme-linked immunosorbent assay (ELISA) at approximately 7, 14, and 28 days after each vaccination, and approximately 3 and 6 months after the third dose.

Analysis Plan:

- a. The proportion of participants with detectable anti-Na-GST-1 and anti-Na-APR-1 (M74) responses will be summarized as a descriptive measure.
- b. Antigen-specific IgG levels will be displayed graphically by study group using notched box plots at each time point.
- c. Geometric mean antibody responses will be compared between vaccine and dose groups at each time point. Comparisons between groups will be made by a one-way

analysis of variance (ANOVA) with pair-wise comparisons between groups made by contrasts.

- d. Percent change in IgG antibody levels from days of vaccination to days 7, 14 and 28 will be compared between vaccine formulation and dose groups. Values will be reported with 95% confidence intervals.
- e. Percent change in IgG antibody levels from vaccination day #1 to #2, and from vaccination day #2 to #3 will be compared between vaccine formulation and dose groups to assess the sustainability of the response from trough to trough. Values will be reported with 95% confidence intervals.
- f. Percent change in IgG antibody levels from the peak following the third vaccination, to 3 and 6 months after the third vaccination. Values will be reported with 95% confidence intervals.
- g. Geometric mean antibody responses for each antigen will be compared using a regression model at each time point with main effects for the doses of *Na-APR-1* (M74) (10, 30 or 100 μ g) and *Na-GST-1* (10, 30 or 100 μ g)
- h. A longitudinal model will be built to describe the IgG levels over time. Using a longitudinal panel model, differences in antibody isotype levels by dose of *Na-APR-1* (M74) and *Na-GST-1* will be explored. This will take account of the correlation between measurements on the same participant.

Tertiary Objective 2: To assess the distribution of IgG subclass responses to *Na-APR-1* (M74) and *Na-GST-1*.

Tertiary Outcome Measure 2: The IgG subclass distribution (IgG1, IgG3, and IgG4) by indirect ELISA approximately 14 days after the third vaccination.

Tertiary Outcome Measure 3: The IgG1-4 subclass distribution by ELISA on each day of vaccination, approximately 28 days later, and approximately 3 and 6 months after the final vaccination.

Analysis Plan:

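### Both antigens are always given at equal doses, so the IgG regression cannot separate their dose effects; no arm supports a single-antigen comparison, and Section 10.1 misdescribes two sample sizes

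*Combined protocol and SAP*

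**What the plan says.** **The regression.** In Section 10.3, item (d) under the secondary objective reads "Geometric mean antibody responses for each antigen will be compared using a regression model with main effects for the doses of Na-APR-1", and goes on to include Na-GST-1 dose, each at 10, 30 or 100 µg. Item (g) under Tertiary Objective 1 repeats this: IgG is "compared using a regression model at each time point with main effects for the doses of" both antigens.

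**The allocation.** Section 3 assigns 16 children in each of three groups to Na-APR-1 at 10, 30 or 100 µg, with the same amount of "Na-GST-1 administered IM in the alternate arm". The remaining 4 per group are "randomized to the control group who will receive HBV co-administered with sterile saline" (Section 4.3.2). Dose groups are not randomised against one another: "Group enrollment will be done in an open sequential fashion" (Section 3).

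**The single-antigen wording.** Section 10.2.1 plans to compare adverse event rates for Na-APR-1 alone and with Na-GST-1. Section 10.3 opens by including a comparison of separate with joint administration in the trial's purpose. Exploratory Objective 1 writes Na-APR-1 +/- Na-GST-1.

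**The sample sizes.** Section 10.1 tabulates the probability of at least one event for N=20, 30 and 60. It describes 20 as the size of each Na-APR-1 dose group. It describes 30 as the number co-administered, as opposed to given Na-APR-1 alone, and labels that column a formulation.

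**Conflicting dose text.** The protocol summary (Description of Interventions, item b) says "Only one dose of Na-GST-1 will be tested". Section 1.2.2 says that the 10, 30 and 100 µg doses of both antigens "were selected for evaluation based on preclinical studies and to maintain an equal fold-increase in the amount of antigen". Section 4.3.3 gives 10 µg to Groups 1 and 2, and then says "Subjects enrolled into Groups 3 and 4 will receive either" 30 µg of each antigen or control. Section 3 has only three groups.

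**The concern.** If two regressors are identical, no data can divide an effect between them. Software would either fail or drop one term and print the joint effect under the other antigen's name, and which antigen is named would be an accident of coding. Section 1.2.3 says that results from this study will help set the doses of the co-formulated product, so a misattributed dose effect could be carried forward.

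Section 1.2.1 calls it a necessary development step to learn whether combining the antigens raises risk or lowers immunogenicity relative to giving each individually. With the wording in Sections 10.2.1 and 10.3, a reader could look for that answer here.

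The detection probabilities in Section 10.1 illustrate the primary aim of estimating vaccine-related adverse event frequency, so the N behind each should be the number of children exposed.

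**Working it through.** **1. Inputs (Sections 3 and 4.3.2).** Vaccinees: 16 at 10/10, 16 at 30/30 and 16 at 100/100 µg, so 3 × 16 = 48. Controls: 3 × 4 = 12 at 0/0. Total 60. Children on one antigen only: 0.

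**2. Rank of the two-dose model.** With intercept *a*, Na-APR-1 dose *x* and Na-GST-1 dose *z*, the model is *a* + *b₁x* + *b₂z*. Here *z* = *x* for every child, so it reduces to *a* + (*b₁* + *b₂*)*x*. Only the sum is estimable. With categorical dose, the Na-GST-1 indicators duplicate the Na-APR-1 indicators.

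| Children | Coding | Columns | Rank |
|---|---|---|---|
| 48 vaccinees | both doses, categorical (1+2+2) | 5 | 3 |
| 48 vaccinees | both doses, linear or log | 3 | 2 |
| 60 with controls | both doses, categorical (1+3+3) | 7 | 4 |
| 60 with controls | both doses, linear | 3 | 2 |
| 48 vaccinees | one dose-level factor | 3 | 3 |
| 60 with controls | one dose-level factor | 4 | 4 |

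A contrast is estimable if adding it as a row leaves the rank unchanged. Neither 30 vs 10 nor 100 vs 10 µg passes for a single antigen; 30/30 vs 10/10 does. As an illustration with invented slopes on log10 dose, the pairs (0.6, 0), (0, 0.6), (0.3, 0.3) and (1, −0.4) all sum to 0.6 and all give fitted values 0.6, 0.886 and 1.2 at the three dose levels, with intercept zero.

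**3. The other reading of the dose text.** If Na-GST-1 were constant, as the summary's item (b) implies, its column would duplicate the intercept among vaccinees (linear coding: 3 columns, rank 2). The Na-APR-1 contrasts would be estimable, and no Na-GST-1 dose contrast among vaccinees would be. With controls added, linear coding has full rank (3 of 3), but the Na-GST-1 term then only contrasts vaccinees with controls. The group mapping in Section 4.3.3 still pairs equal doses, so step 2 applies to it as well.

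**4. Detection probabilities.** The formula is 1 − (1 − *p*)^N. It reproduces all 15 cells of the Section 10.1 table; for example, 1 − 0.95^30 = 78.54% and 1 − 0.90^20 = 87.84%. The arithmetic is right and the description of N is wrong. With the allocated counts:

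| True rate | N=20 (plan) | N=16 per dose | N=30 (plan) | N=48 co-administered |
|---|---|---|---|---|
| 0.5% | 9.54% | 7.71% | 13.96% | 21.38% |
| 1% | 18.21% | 14.85% | 26.03% | 38.27% |
| 3% | 45.62% | 38.57% | 59.90% | 76.82% |
| 5% | 64.15% | 55.99% | 78.54% | 91.47% |
| 10% | 87.84% | 81.47% | 95.76% | 99.36% |

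In the plan's two worked examples, the per-dose figure is too high by 87.84 − 81.47 = 6.37 points, and the co-administration figure is too low by 91.47 − 78.54 = 12.93 points.

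**The case against.** **Item (d) could mean one model per antigen**, with anti-Na-APR-1 IgG on Na-APR-1 dose and anti-Na-GST-1 IgG on Na-GST-1 dose. Each such model has full rank. But the two dose variables are the same, so each model estimates the joint dose-level effect under a different name. The detailed analytical plan promised in Section 10.3 cannot cure this either, because the confounding lies in the allocation.

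**A reader might infer that the secondary objective cannot be met.** The documents do not support that. The objective concerns co-administered doses, and the one-way ANOVA across dose groups in item (c) is estimable and addresses it, within the limits of sequential groups and the stated lack of power. Fitted dose-group means are unaffected, and the primary safety analysis does not use this regression.

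**A reader might infer that 48 is the only possible value for the N=30 column.** That is too strong. Thirty is the number of children per vaccination schedule (3 × 10, controls included), so the column could stay under that label. It is not the co-administration count.

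**The 20-versus-16 point is partly wording.** Twenty is the size of an enrolled group. Section 10.1 treats 80% or more as high, and 81.47% still meets that, so its conclusion for common events stands. The halting rules in Section 8.5 count participants and use neither figure.

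**The single-antigen wording looks like leftover text.** Section 2.1 has no such objective, and most of the listed analyses compare hookworm with hepatitis B vaccine or compare doses. That limits the harm, but Section 10.3 still states the comparison as part of the trial's purpose.

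**Conclusion.** The point holds, with modest consequence, and should be fixed. On the Section 3 allocation, items (d) and (g) cannot separate the antigens' dose effects under categorical, linear or log coding, and attributing the joint effect to one antigen would be arbitrary. The comparison with single-antigen administration has no children on one side. Section 10.1 attaches 30 and 20 to populations of 48 and 16, which moves its two examples to 91.47% and 81.47%.

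The rank result assumes the equal-dose allocation in Section 3. If Na-GST-1 were constant, only its own dose contrasts among vaccinees would be lost. The absence of a single-antigen arm and the counts of 48 and 16 do not depend on which dose statement prevails. The probabilities treat children as independent with a common event rate, as the plan's table does, and make no allowance for dropout.

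**What to change.** 1. In Section 10.3, secondary item (d) and Tertiary Objective 1 item (g), replace the two dose main effects with one joint dose-level trend (for example in log dose) for each antigen's log IgG. Alternatively, delete both items: a single categorical dose factor would only repeat the ANOVA in the two items (c). Read dose as joint dose level in the longitudinal models (Tertiary Objective 1 item h, Tertiary Objective 2 item d). State that separate antigen dose effects are not estimable under equal doses.
2. Delete the alone/separate wording in Sections 10.1, 10.2.1 and 10.3 and the +/- in Exploratory Objective 1. In secondary item (c) and Tertiary Objective 1 items (d) and (e), drop the word formulation so that comparisons are by vaccine and dose group, as other items already say. In Section 10.2.1, compare adverse event rates by vaccine (hookworm vs hepatitis B) and by dose level.
3. In Section 10.1, give N=16 per dose and N=48 for co-administered children, using the columns above, and revise the two worked examples. Keep N=60 as all participants. Keep N=30 only if relabelled as all children per vaccination schedule, controls included.
4. State that the trial cannot test interference against single-antigen administration.
5. Reconcile the summary's single Na-GST-1 dose with the summary's own group allocation, Sections 1.2.2, 3, 4.3.3 and 5.1.2.2, and items (d) and (g) of Section 10.3. Reconcile the group-to-dose mapping in Section 4.3.3 with Section 3. If the result is a constant Na-GST-1 dose, state instead that no Na-GST-1 dose contrast among vaccinees is estimable.

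The cost is protocol and analysis-plan wording plus two recomputed table columns. Sample size and data collection do not change.
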